3.1 Device Instructions

Instructions for use:

1. Hold the SinuSonic device at a 45-degree angle
2. Deep breathe

3. Hold the SinuSonic to your nose and blow out into the mask of the SinuSonic. The goal here is to hear the “target flutter” sound that is desired during treatment with the SinuSonic
4. Put the device over the nose using the nasal mask
5. Breathe in and out thru the nose if possible. If nasal breathing is not possible it is ok to open mouth to breathe in and try and hear the “target flutter” sound when you breathe out
6. You will feel a little resistance to breathe out and a vibration sensation from a speaker in the device
7. Remove the device to “blow the nose” if nasal drainage occurs
8. Return the device to the nose then breathe in and out thru the nose to try and hear the “target flutter” sound
9. Time of use is 3 minutes of nasal breathing with the device - as tolerated

3.2 Device Usage and Safety

The SinuSonic consists of a fully-disposable medical grade silicone nosepiece mounted to a resin body. The device is equipped with a flutter valve located at the top of the device which creates gentle, self-guided oscillating expiratory resistance.

4.0 Inclusion and Exclusion Criteria/ Study Population

Aim 1 exhaled NO: For the exhaled NO portion of the study, we will examine 10 healthy control patients with no symptoms of upper airway infection, inflammation or ETD to determine impact of SinuSonic upon NO release.

Inclusion Criteria

- -Adults 18 years or older with no symptoms of URI, ETD or other ENT conditions

Exclusion Criteria

- Sinonasal or ear surgery within last 3 months (including balloon ET dilation)
- Any ENT condition that may impact upper airway to include sinusitis, otitis, or allergies
- Upper respiratory illness within last 2 weeks
- Topical decongestant use in last week
- Current nasal crusting or ulceration on rhinoscopy
- History of severe nose bleeding within last 3 months
- Known pregnancy
- Allergic sensitivity to silicone or any other component of device
- Inability to read and understand English
- Inability to perform treatment due to underlying medical condition

Aim 2 ETD efficacy: The ETD study population will consist of individuals presenting for care at the Otolaryngology clinics at the Medical University of South Carolina with ETD, or from the community at large.

Inclusion Criteria

- -Adults 18 years or older with diagnosis of ETD by an otolaryngologist

- ≥ 6 months of symptoms duration
- ≥ 3 ETD symptoms (ear pressure, feeling that ears are clogged, cracking/popping of ears, muffled hearing, tinnitus)
- ETDQ-7 score ≥ 3
- Audiogram within the last year

Exclusion Criteria

- Sinonasal or ear surgery within last 3 months (including balloon ET dilation)
- Indwelling ear tubes
- Tympanic membrane perforation
- Hx of cholesteatoma, mastoidectomy, tympanoplasty, or ossicular chain reconstruction
- Patulous ET
- Hx of Meniere's disease
- Moderate or severe nasal valve collapse
- Grade 3-4 polyps
- Upper respiratory illness within last 2 weeks
- Topical decongestant use in last week
- Current nasal crusting or ulceration on rhinoscopy
- History of severe nose bleeding within last 3 months
- Known pregnancy
- Allergic sensitivity to silicone or any other component of device
- Inability to read and understand English
- Inability to perform treatment due to underlying medical condition

Aim 3 Facial pain/pressure efficacy: The facial pain/pressure study population will consist of individuals presenting for care at the Otolaryngology clinics or community at large with self-reported sinus pain/pressure.

Inclusion Criteria

- -Adults 18 years or older who complain of facial pain or pressure
- ≥ 3 months of symptoms duration (can be intermittent)
- Pain/pressure VAS score ≥ 5

Exclusion Criteria

- Sinonasal surgery within the last 3 months
- Grade 3-4 polyps
- Upper respiratory illness within last 2 weeks
- Topical decongestant use in last week
- Current nasal crusting or ulceration on rhinoscopy
- History of severe nose bleeding within last 3 months
- Known pregnancy
- Allergic sensitivity to silicone or any other component of device
- Inability to read and understand English
- Inability to perform treatment due to underlying medical condition

5.0 Number of Subjects

Aim 1, exhaled NO: We anticipate 10 healthy control subjects for the exhaled NO portion of the study.

Aim 2, ETD: This is a pilot study. The anticipated ETD study population is 30 subjects.

Aim 3, Facial pain/pressure: This is a pilot study. The anticipated facial pain/pressure study population is 30 subjects.

6.0 Setting

Research will be conducted at the Medical University of South Carolina. Potential participant screening for all subjects across all aims, as well as baseline evaluations, will occur in the outpatient ENT clinics. For AIM 2, the 6-week post treatment assessment will take place in the outpatient ENT clinics. For AIM 3, follow-up measures will be collected remotely using REDCap at 2 and 4 weeks.

7.0 Recruitment Methods

MUSC Otolaryngologists will notify the study coordinator (SC) of potential participants through the ENT Clinic. If the patient is interested, the coordinator will approach them and explain the study in further detail and begin the informed consent process.

8.0 Consent Process

Patients who are deemed eligible for this study will be approached by the Principal Investigator or Co-Investigator in the ENT Clinic at the Medical University of South Carolina about the study. A member of the study team will describe in full detail the study and the informed consent form to the potential subject. The prospective participant will be given adequate time to review the informed consent form and ask any questions that they have before the consent is obtained. Participants will be given a signed copy of the ICF.

8.1 Withdrawal

At any point during the study, a subject may withdraw from the study.

9.0 Study Design / Methods

This study is designed as a pilot study.

Data will be collected by the study investigators as well as the subjects themselves throughout the entirety of the study. The data will consist of answers from subjects for questionnaires asked by the clinicians as well as self-reported answers from the subjects.

Safety will be monitored throughout the study based on monitoring of adverse events, performing nasal, measuring vital signs (i.e. blood pressure, pulse) and weight, and through collection of concomitant medication information.

The period of observation for collection of non-serious adverse events extends from the time the subject gives informed consent until completion of the End-of-study visit or Early Termination Visit. Serious adverse events (SAE) will be reported from the time of informed consent through 30 days after the last use of the SinuSonic. Adverse event data listings will be reviewed by SinuSonic at regular intervals throughout the study. In

addition, SinuSonic will be alerted of Adverse Events of interest via automated emails programmed in the EDC system. Patient compliance will be assessed via weekly phone calls from study coordinator.

9.1 Schedule of Events

Aim 1: NO in N=10 controls	Screening and baseline assessment
Day	0
Informed consent	X
Inclusion/exclusion criteria	X
Medical history	X
Rhinology, otoscopy	X
Vital signs	X
Exhaled nasalNO at 30 seconds and 5 min	X

Aim 2: ETD efficacy in N=30 patients	Screening and baseline assessment	Primary timepoint for outcomes
Week	0	6 + 1
Informed consent	X	
Inclusion/exclusion criteria	X	
Medical history	X	
Rhinology, otoscopy	X	X
Vital signs	X	
Distribution of Sinusonic	X	X
ETDQ-7	X	X
ETD VAS questionnaire	X	X
Tympanogram	X	X

Aim 3: Facial pain/pressure in N=30 patients	Screening and baseline assessment	Primary timepoint for outcomes	Secondary timepoint for outcomes
Week	0	2	4
Informed consent	X		
Inclusion/exclusion criteria	X		
Medical history	X		
Rhinology, otoscopy	X		

Vital signs	X		
Distribution of Sinusonic	X		
Pain/pressure VAS	X	X	X
BPI-SF	X	X	X
MPQ-SF	X	X	X

10.0 Data Management

All analyses and graphs will be performed with SPSS 24.0, Sample Power 3.0, and Sigma Plot 10.0 (SPSS, Chicago, IL.). Disease information and demographic variables, such as age, gender, race, quality of life (QOL) scores, and VAS scores will be summarized using frequencies, means, and standard deviation as appropriate. Aim 1 nasal NO metrics will be compared between baseline vs 10 seconds and baseline vs 3 minutes. Aim 2 metrics (ETDQ-7, ETD VAS and tympanogram) will be compared between baseline and 6 weeks. Aim 3 metrics (VAS, BPI-SF, MCQ-SF) will be compared between baseline vs 2 weeks and baseline vs 4 weeks. Categorical variables will be compared using Chi Square or McNemar's test. Continuous variables will be compared using One-Way ANOVA with repeated measures follow by post-hoc analysis. Data regarding safety and patient satisfaction will be summarized for each time point. A p-value ≤ 0.05 will be considered statistically significant. Due to the exploratory nature of this study, no p-value correction (ie Bonferroni) will be applied.

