1.0 Objectives / Specific Aims

Aim 1: To determine if combined acoustic vibration and oscillating expiratory pressure impacts exhaled nasal Nitric Oxide (NO) in healthy controls as a potential mechanism

Aim 2: To determine the safety and efficacy of combined acoustic vibration and oscillating expiratory pressure for treatment of eustachian tube dysfunction (ETD).

Aim 3: To determine the safety and efficacy of combined acoustic vibration and oscillating expiratory pressure for treatment of sinus pain/pressure

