3.0 Intervention to be studied

Aim 1: Exhaled NO in healthy controls (N=10)

- Initial intervention: Baseline exhaled nasal NO will be measured using a clinically available nasal airflow sampling device at rest. Then using SinuSonic devices for 2 exhalations followed by the 30 second NO sampling period. We will use 4 SinuSonic devices with frequencies between 64Hz and 2,000Hz in random order. Five minutes rest will be allowed between trials. The final trial will use 128 Hz for 1 minute.

Aim 2: Clinical efficacy in subjects with ETD (N=30)

- Baseline: Subjects will complete ETD questionnaire to confirm eligibility. Tympanogram will be completed. After confirming eligibility, subjects will use the SinuSonic device for 3 minutes in the clinic setting. Immediate treatment effect will be assessed with questionnaires.
- Primary timepoint: Subjects will use SinuSonic device twice daily for 3 minutes in the home setting for 6 weeks. Tympanogram and ET questionnaires will be completed.

Aim 3: Clinical efficacy in subjects with sinus pain/pressure (N=30)

- Baseline: Subjects will complete VAS to confirm eligibility. After confirming eligibility, subjects will use the SinuSonic device for 3 minutes in the clinic setting. Immediate treatment effect will be assessed with questionnaires.
- Primary timepoint: Subjects will use SinuSonic device twice daily for 3 minutes in the home setting for 4 weeks. Questionnaires will be completed at 2 weeks and 4 weeks.

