COMORBID MEDICAL CONDITIONS: Check box and provide details if present

- ☐ Depression history: ☐ Resolved/past diagnosis ☐ Present/medicated ☐ Present/not medicated
- ☐ Anxiety history: ☐ Resolved/past diagnosis ☐ Present/medicated ☐ Present/not medicated
- ☐ Obstructive Sleep Apnea: ☐ Currently being treated ☐ History / No current treatment
- ☐ Allergic rhinitis: _____
- ☐ Previous allergy testing (blood test or skin prick): ☐ Yes ☐ No
- ☐ Immunotherapy shots for allergies: ☐ Yes ☐ No ☐ Currently
- ☐ Non-allergic rhinitis ☐ Yes ☐ No
- ☐ Asthma ☐ Yes ☐ No
- ☐ Chronic rhinosinusitis ☐ Yes ☐ No
- ☐ Nasal polyps ☐ Yes ☐ No
- ☐ Viral upper respiratory infection ☐ Yes ☐ No
- ☐ Prior ear/sinus surgery ☐ Yes ☐ No
- ☐ Migraine headache history: ☐ Resolved/past diagnosis ☐ Present/medicated ☐ Present/not medicated

- _____
- ☐ Height (ft/in): _____
- ☐ Weight (lbs): _____

Rhinoscopy:

Septal Deviation: None Mild Moderate Severe Nasal

valve collapse: None Mild Moderate Severe Bleeding:

None Yes

Crusting: None Yes

Otoscopy: Normal Abnormal findings: _____

Baseline exhaled NO measurements

Resting peak: _____

10 second peak: _____

3 minute peak: _____

AIM 1: DAY 1 REPEAT EXAMINATION

Rhinoscopy:

Septal Deviation: None Mild Moderate Severe Nasal
valve collapse: None Mild Moderate Severe Bleeding:

Crusting: None Yes
None Yes

Otoscopy: Normal Abnormal findings: _____

Day 1 exhaled NO measurements

Resting peak: _____

10 second peak: _____

3 minute peak: _____

Day 1 patient satisfaction/safety

How much pain did you experience using device? None Mild Moderate Severe

Would you use device again? Yes No

Would you recommend device to others? Yes No

AIM 2, ETD: Patient Medical History and exam

SinuSonic Study

PI: [name]

Subject ID#: _____ Subjects Initials: _____

DEMOGRAPHIC AND CLINICAL VARIABLES (If not previously collected):

Age at enrollment (years):

--	--

Gender: Male Female

What is/was your profession (current/retired)? _____

LANGUAGE, ETHNICITY, RACE, MARITAL STATUS

Please mark one of the following categories which describes your native language:

- ☐ American English
- ☐ Other: please specify _____

Please mark one of the following categories which describes your ethnicity:

- ☐ Not Hispanic or Latino
- ☐ Hispanic or Latino

Please mark one or more of the following categories which describes your race:

- ☐ American Indian or Alaska Native
- ☐ Asian
- ☐ Black or African American
- ☐ Native Hawaiian or Other Pacific Islander
- ☐ White

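### The Aim 1 nitric oxide measurements are described in three incompatible ways, and the randomised frequency factor is neither recorded on the form nor used in a planned contrast

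*Combined protocol and SAP*

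**What the plan says.** Aim 1 (section 1.0) is "To determine if combined acoustic vibration and oscillating expiratory pressure impacts exhaled nasal Nitric Oxide (NO) in healthy controls as a potential mechanism". On sample size, section 5.0 says "We anticipate 10 healthy control subjects for the exhaled NO portion of the study".

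The measurements are described in four places:

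- **Section 3.0 (procedure).** A resting reading is taken first. The device step is "Then using SinuSonic devices for 2 exhalations followed by the 30 second NO sampling period", and "We will use 4 SinuSonic devices with frequencies between 64Hz and 2,000Hz in random order". Trials are separated by five minutes of rest, and "The final trial will use 128 Hz for 1 minute".
- **Section 9.1 (schedule).** The Aim 1 table has a single column, Day 0, with the entry "Exhaled nasalNO at 30 seconds and 5 min".
- **Section 10.0 (analysis).** "Aim 1 nasal NO metrics will be compared between baseline vs 10 seconds and baseline vs 3 minutes". Continuous variables in general go to a repeated-measures ANOVA with post-hoc tests. No frequency factor is named.
- **Appendix, Aim 1 form.** There are three fields: a resting peak, a peak at 10 seconds and a peak at 3 minutes. The same three fields appear again under "AIM 1: DAY 1 REPEAT EXAMINATION".

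Section 15.0 pays $50 per visit and caps the control group at $50.

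**The concern.** The analysis names two post-baseline values that the procedure does not generate, and it is silent on the values that the procedure does generate. Site staff who follow section 3.0 will have readings with nowhere to put them. Staff who follow the form will collect something that section 3.0 does not describe.

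The loss would fall mainly on frequency, the only randomised element in Aim 1. Section 2.0 bases the proposed mechanism on acoustic energy. Rest versus device changes the sound, the mask and the expiratory resistance together, whereas the comparison between frequencies varies the sound under the same brief manoeuvre. If the frequency belonging to each reading is not written down at the visit, it may not be recoverable afterwards.

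A second, smaller matter is order. The 1-minute trial always comes last, so any effect of longer exposure is mixed with whatever the four preceding trials leave behind.

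**Working it through.** The plan gives no effect size, standard deviation or power for Aim 1, so there is no figure to reproduce. The check is a side-by-side comparison and a count.

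**1. Conditions and times in each place**

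| Place | Resting reading | Post-baseline conditions or times | Frequency identified | Visits |
|---|---|---|---|---|
| Section 3.0 | one, first | four short trials with 30-second sampling; one 1-minute trial at 128 Hz | yes | not stated |
| Section 9.1 | not listed separately | 30 seconds; 5 minutes | no | Day 0 |
| Section 10.0 | baseline | 10 seconds; 3 minutes | no | not stated |
| Appendix form | resting peak | 10 seconds; 3 minutes | no | baseline and Day 1 |

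Sections 3.0 and 10.0 share no post-baseline time. Section 10.0 and the form agree with each other, which leaves three versions. Neither section 10.0 nor the form says whether 10 seconds and 3 minutes are durations of use or times after use.

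**2. Readings against fields, if section 3.0 is run**

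- Device readings per subject: 4 + 1 = 5. For 10 subjects: 5 × 10 = 50.
- Device fields per subject on the Day 0 form: 2. For 10 subjects: 2 × 10 = 20.
- Device readings with no field: at least 50 − 20 = 30.
- Fields labelled by frequency or trial order: 0.
- Planned contrasts that use frequency: 0 of 2.

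With the resting reading included, the procedure gives 6 readings per subject and the Day 0 form has 3 fields. The Day 1 form brings the fields to 6, but they repeat the same labels and belong to another visit, so the equal count does not help.

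**3. Number of visits for controls**

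Section 15.0 implies $50 ÷ $50 = 1 paid visit, in line with the Day 0-only schedule. The Day 1 form conflicts with both.

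**4. Order**

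Rest is always first, the four frequency trials occupy the next four places in random order, and the 1-minute trial is always last. The order of the four frequencies is therefore protected by randomisation, but exposure length is not separated from position.

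This also limits the model. With 10 subject terms, 5 condition terms (six conditions) and 5 categorical position terms (six positions), there are 10 + 5 + 5 = 20 columns. The rest condition is identical to the first position and the 1-minute condition is identical to the last, so two columns are redundant and the rank is 20 − 2 = 18. Device versus rest cannot then be estimated. A linear position term gives 10 + 5 + 1 = 16 columns, and its slope can be estimated from the randomised trials.

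**The case against.** The strongest reply is that section 10.0 and the form agree exactly, so the planned tests have a place for their data, and that the aim asks about the combined device and does not mention frequency. Rest versus device is the direct contrast for that aim. The general repeated-measures ANOVA could accommodate several within-subject conditions. A 10-second value could be read within the 30-second sampling window, and the schedule's 30 seconds and 5 minutes may echo the sampling period and the rest interval. The Day 1 form may be a leftover. This is also a 10-subject part of a declared pilot, with testing described as exploratory.

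Much of this stands, and it limits the point. A reader might infer that the planned tests have no data. That is so only if section 3.0 is followed and the form is not. A reader might also infer that the mechanism aim cannot be answered. The documents do not support that, because a before-and-after comparison can address the aim once the sections agree.

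The rest does not remove the conflict. No text links the 10-second value to the sampling window or the schedule's times to the procedure, and nothing in section 3.0 yields a 3-minute value. The ANOVA sentence names no frequency factor, and the form would not hold the data for one. Pilot status excuses a small sample and uncorrected p-values, but not undefined measurements.

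**Conclusion.** The point holds as a conflict between the procedure, the schedule and the analysis with its form. The Aim 1 analysis is wrong as written: its 3-minute contrast has no counterpart in section 3.0, and its 10-second contrast has none that is stated. If section 3.0 is run, at least 30 of 50 device readings have no field on the Day 0 form, and the randomised factor is neither recorded nor analysed. These counts assume one reading per trial, all 10 subjects completing all five device trials, and the form used as printed.

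Exposure length is confounded with order by design. A reader might infer a definite bias in the 1-minute reading, for instance from depletion over successive trials. The documents give no depletion or carry-over rate, they provide five minutes of rest between trials, and no comparison of the 1-minute trial with the earlier trials is planned. The size of any order effect is therefore unknown and could be nil.

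The documents do not show which of the three versions is intended.

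**What to change.** **Needed whichever version is intended.** Reconcile sections 3.0, 9.1 and 10.0 and the appendix form to one list of nitric oxide conditions and visits. State for each time whether it is a duration of use or a time after use. Either delete the Day 1 form, or add the visit to section 9.1 and bring section 15.0 into line.

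**If section 3.0 is what is run:**

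1. List the four frequencies and say whether 128 Hz is one of them. Give the form one row per trial: sequence position, frequency, exposure and peak nitric oxide.
2. Replace the Aim 1 sentence in section 10.0 with within-subject contrasts of each device condition against rest and between the four frequencies. Either a repeated-measures ANOVA or a mixed model with subject as a random effect will serve.
3. Do not enter trial position as a categorical factor. Use a linear term or leave it out. A linear term is learned from the four randomised trials and extrapolated to the first and last positions, and the report should say so.
4. Optionally, take a short resting reading at the end of each of the four existing rests and use it as the next trial's own baseline, with the initial resting reading serving the first trial. Without this, report the 1-minute result as confounded with order.

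**Cost.** Protocol wording and one form page, with no extra subjects. The optional step adds four short readings per subject, or 4 × 10 = 40 in all, within rests already planned. The changes should be in place before the first control is measured.

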- ☐ Other

SMOKING HISTORY1. Do you **currently** smoke tobacco products? Yes No (If No please go to question 2)

How many tobacco products do you use in a day? _____ Singles Packs

CURRENT MEDICATION USAGE

- | | | |
|---|------------------------------|-----------------------------|
|  Nasal steroid sprays (Flonase, Nasonex, etc) |  Yes |  No |
|  Nasal antihistamine spray (Astelin, etc) |  Yes |  No |
|  Oral antihistamines (Allegra, Claritin, Benedryl, etc) |  Yes |  No |
|  Oral decongestant (Sudafed, etc) |  Yes |  No |
|  Mucolytic (Mucinex, etc) |  Yes |  No |
|  Luekotriene (Singulair, etc) |  Yes |  No |

COMORBID MEDICAL CONDITIONS: Check box and provide details if present

- ☐ Depression history: ☐ Resolved/past diagnosis ☐ Present/medicated ☐ Present/not medicated
☐ Anxiety history: ☐ Resolved/past diagnosis ☐ Present/medicated ☐ Present/not medicated
☐ Obstructive Sleep Apnea: ☐ Currently being treated ☐ History / No current treatment
☐ Allergic rhinitis: _____
☐ Previous allergy testing (blood test or skin prick): ☐ Yes ☐ No
☐ Immunotherapy shots for allergies: ☐ Yes ☐ No ☐ Currently
☐ Non-allergic rhinitis ☐ Yes ☐ No
☐ Asthma ☐ Yes ☐ No
☐ Chronic rhinosinusitis ☐ Yes ☐ No
☐ Nasal polyps ☐ Yes ☐ No
☐ Viral respiratory infection ☐ Yes ☐ No
☐ Prior ear/sinus surgery ☐ Yes ☐ No
☐ Migraine headache history: ☐ Resolved/past diagnosis ☐ Present/medicated ☐ Present/not medicated

- _____
☐ Height (ft/in): _____
☐ Weight (lbs): _____

Rhinoscopy:

Septal Deviation: None Mild Moderate Severe Nasal
valve collapse: None Mild Moderate Severe Bleeding:

Crusting: None Yes
 None Yes

Otoscopy: ☐Normal ☐Retracted no effusion ☐Effusion

Valsalva: ☐Successful ☐Not successful

Tympanogram type: A B C

AIM 2, ETD: Baseline Questionnaires

PATIENT QUESTIONS	
How long have you had eustachian tube problems? <3 months 3-6 months 6-12 months 1-3 year >3 years	
OVER THE LAST FEW MINUTES, HOW TROUBLESOME HAVE THE FOLLOWING SYMPTOMS BEEN? PLEASE PLACE A MARK ON THE LINE.	
	Not troublesome Worst thinkable/troublesome

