Ear pressure	◆—————◆
Feeling that ears are clogged	◆—————◆
Cracking/popping of ears	◆—————◆
Muffled hearing	◆—————◆
Tinnitus (noise in ears)	◆—————◆
OVERALL ASSESSMENT OF EAR and EUSTACHIAN TUBE PROBLEMS	◆—————◆

BASELINE ETDQ-7

Next to each question, circle the number that best describes how you feel.

During the past 1 month, how much of a problem was each of the following?	No problem		Moderate Problem			Severe Problem	
Pressure in the ears?	1	2	3	4	5	6	7
Pain in the ears?	1	2	3	4	5	6	7
A feeling that your ears are clogged or "under water"?	1	2	3	4	5	6	7
Ear problems when you have a cold or sinusitis?	1	2	3	4	5	6	7
Crackling or popping sounds in the ears?	1	2	3	4	5	6	7
Ringing in the ears?	1	2	3	4	5	6	7
A feeling that your hearing is muffled?	1	2	3	4	5	6	7

Do you get these symptoms in one ear only or both ears?

Left ear only

Right ear only

Both ears

INCLUSION CRITERIA (all must be yes):

Does patient have ETD sx for ≥ 6 mos? Yes No

Is ETDQ-7 score ≥ 3 ? Yes No

Does patient have ≥ 3 ETD symptoms above? Yes No

AIM 2, ETD: Follow Up Questionnaire 5 minutes**FOLLOW UP ETD VAS 5 MINUTES**

OVER THE LAST FEW MINUTES, HOW TROUBLESOME HAVE THE FOLLOWING SYMPTOMS BEEN? PLEASE PLACE A MARK ON THE LINE.	
	Not troublesome Worst thinkable/troublesome
Ear pressure	◆—————◆
Feeling that ears are clogged	◆—————◆
Cracking/popping of ears	◆—————◆
Muffled hearing	◆—————◆
Tinnitus (noise in ears)	◆—————◆
OVERALL ASSESSMENT OF EAR and EUSTACHIAN TUBE PROBLEMS	◆—————◆

AIM 2, ETD: 6-Week Follow Up Questionnaires

Objective Evaluation			
Rhinoscopy:			
Bleeding:	None	Yes	
Crusting:	None	Yes	
Otoscopy:	 Normal	 Retracted no effusion	 Effusion
Valsalva:	 Successful	 Not successful	
Tympanogram type:	A	B	C

OVER THE LAST FEW MINUTES, HOW TROUBLESOME HAVE THE FOLLOWING SYMPTOMS BEEN? PLEASE PLACE A MARK ON THE LINE.		
	Not troublesome	Worst thinkable/troublesome
Ear pressure		
Feeling that ears are clogged		
Cracking/popping of ears		
Muffled hearing		
Tinnitus (noise in ears)		
OVERALL ASSESSMENT OF EAR and EUSTACHIAN TUBE PROBLEMS		

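### Aim 2 tympanogram: section 10 names no paired test that fits the three recorded types, and the forms do not record which ear the type belongs to

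*Combined protocol and SAP*

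**What the plan says.** Section 10.0 (Data Management) sets the comparison: "Aim 2 metrics (ETDQ-7, ETD VAS and tympanogram) will be compared between baseline and 6 weeks". Aim 2 is a single group, so this is a within-patient comparison. For categorical data the section says: "Categorical variables will be compared using Chi Square or McNemar's test". It does not say which test goes with which variable.

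The Aim 2 baseline examination form in the appendix records the result on one line: "Tympanogram type: A B C". The 6-week form has the same single line ("Tympanogram type", with the same three letters). Neither line has a left/right field.

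Side is asked elsewhere, after the ETDQ-7 at both visits: "Do you get these symptoms in one ear only or both ears". The answers are left, right or both. Nothing links that answer to the tympanogram.

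On size and error rate: "The anticipated ETD study population is 30 subjects" (section 5.0), "A p-value ≤ 0.05 will be considered statistically significant" and "no p-value correction (ie Bonferroni) will be applied" (both section 10.0).

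**The concern.** There are two gaps.

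**The test.** Every comparison listed in section 10.0 is before-after within the same subjects. A Chi Square for independent groups fits none of them. McNemar's test respects the pairing but works on two categories, and the recorded outcome has three. No section collapses A/B/C to two levels or names a three-level paired test.

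**The ear.** Each patient has two ears and one letter per visit. No rule says which ear supplies the letter, how two ears are combined, or that the same ear is used at week 6. A test can be corrected after the data are in, but the forms cannot show which ear was recorded.

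The tympanogram is the only objective Aim 2 metric that section 10.0 lists for comparison. Otoscopy and Valsalva are on the same forms but are not on that list. The other two listed Aim 2 metrics are patient-reported, in a study without a control group.

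**Working it through.** **Inputs.** From the documents: 30 patients in one group (section 5.0); two visits (section 9.1); threshold 0.05 with sidedness not stated, taken here as two-sided (section 10.0); three types and no ear field (appendix). The documents give no power, effect size or tympanogram rates, so there is no figure to reproduce. Every rate below is an assumption.

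**1. The unstated choice can decide the result.** Take an illustrative table of 30 patients: 12 type A stay A; of 6 type B, 2 become A; of 12 type C, 6 become A. The margins go from 12/6/12 to 20/4/6.

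| Analysis | Calculation | p |
|---|---|---|
| Chi Square, visits treated as independent | 8²/32 + 2²/10 + 6²/18 = 4.4, 2 df | 0.111 |
| Bowker symmetry test (not named in the plan) | 2²/2 + 6²/6 = 8, 3 df | 0.046 |
| Exact McNemar, A vs B/C | 8 changes one way: 2 × 0.5⁸ | 0.008 |
| Exact McNemar, B vs A/C | 2 changes one way: 2 × 0.5² | 0.50 |

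**2. Power on the two-level outcome.** Assume 50% abnormal (B or C) at baseline, 25% at week 6, and 2% newly abnormal. The cell probabilities are:

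- abnormal at both visits: 0.25 − 0.02 = 0.23
- abnormal to normal: 0.50 − 0.23 = 0.27
- normal to abnormal: 0.02
- normal at both visits: 0.48

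With r and s patients abnormal at the two visits and t = (r + s)/60, the unpaired Chi Square statistic is (r − s)²/[60 t(1 − t)] on 1 df, without continuity correction. Exact McNemar uses the binomial on the changed pairs. Summing the multinomial probabilities over all tables of 30 gives power of **51.8% for Chi Square and 68.9% for exact McNemar**.

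**3. Rejection rate when nothing changes.** With abnormal rate π at both visits and within-patient correlation ρ, each change cell has probability π(1 − π)(1 − ρ). For π from 30% to 50%:

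| ρ | Chi Square | Exact McNemar |
|---|---|---|
| 0.3 | 1.9–2.0% | 2.1–2.3% |
| 0.5 | 0.6% | 1.4–1.8% |

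Both are well below 5%. At ρ = 0.3 they barely differ.

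**4. Dependence on abnormal baselines.** With all changes one way, exact McNemar gives 2 × 0.5⁵ = 0.0625 for five changes and 2 × 0.5⁶ = 0.031 for six, so six are needed. If half of the abnormal patients normalise and none worsen, power is P(Binomial(m, 0.5) ≥ 6): 0.849 for m = 15, 0.613 for m = 12 and 0.254 for m = 9. Aim 2 eligibility (section 4.0) does not require an abnormal tympanogram, so m is not controlled. Each abnormal ear missed at baseline lowers it.

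**5. What an unidentified ear does.** Take a patient whose affected ear is C at both visits and whose other ear is A.

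| Ear at baseline / week 6 | Recorded | Effect |
|---|---|---|
| Affected / affected | C, C | Correct: no change |
| Other / other | A, A | Uninformative; would also hide a real change |
| Affected / other | C, A | False improvement |
| Other / affected | A, C | False worsening |

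Switches that are equally likely in either direction add noise. Switches mostly in one direction would bias the result.

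**The case against.** Section 10.0 can be read as a generic menu: Chi Square for independent data, McNemar for paired data. On that reading the paired option is already named, and no sentence assigns Chi Square to the tympanogram. This has force, but no independent-group comparison is planned, and the reading still leaves three categories with no stated split.

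A reader might infer that the outcome cannot be analysed by McNemar at all. The documents do not support that: A/B/C can be collapsed, or an extension such as Bowker's test used. The defect is that neither is specified.

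A reader might also infer that Chi Square would produce false efficacy claims. Step 3 shows that the unpaired version errs in the conservative direction. A Chi Square of association on the baseline-by-week-6 table is different. It tests whether the visits are related, and it rejected in 87–100% of simulated tables with no net change (assumed A/B/C mix of 40/20/40%). But the plan does not say that Chi Square would be applied that way.

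On the ear, symptom side is collected at both visits, which helps with one-sided patients if staff tested the symptomatic ear. The documents do not say that they did, and a patient with symptoms in both ears still has one letter and no rule. Equally, nothing shows that wrong ears were recorded. The point is that nobody could tell.

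Finally, this is an exploratory pilot with no p-value correction, and the tympanogram is one of three Aim 2 metrics. That excuses modest power. It does not excuse an undefined test or an unidentified ear.

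**Conclusion.** The point holds as an under-specified analysis combined with a data-collection gap. The test can be corrected at any time before analysis. The missing ear cannot be recovered from the forms, so it is the more pressing part.

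Under the assumed fall from 50% to 25% abnormal, choosing Chi Square over exact McNemar costs about 17 percentage points of power (68.9 − 51.8). That figure depends on the assumed rates and shows direction and rough size only. The effect of ear mix-ups cannot be sized, because the documents do not say how the recorded ear is chosen.

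A broader claim, that the tympanogram is the only objective measure in Aim 2, would go too far, because otoscopy and Valsalva are also recorded. Given the exploratory setting this should be changed, but it does not undermine the study as a whole.

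**What to change.** 1. On both Aim 2 forms, replace the single tympanogram line with one line for each ear.
2. In section 10.0, fix the analysis ear at baseline: the symptomatic ear or, if symptoms are in both, the worse ear on the baseline tympanogram, with a stated rule for ties. Use the same ear at week 6.
3. Name the main test: type A versus B/C by exact McNemar, two-sided. Add a marginal-homogeneity test of the three-level table (Stuart-Maxwell) as supportive.
4. Delete Chi Square for before-after comparisons.

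**Cost.** One extra field per ear at two visits and a few sentences in section 10.0; no extra visits or patients. The A versus B/C split does not distinguish B from C, so a move between them counts as no change in the main test. Choosing the worse ear at baseline also invites some regression to the mean in bilateral patients. Because both ears would be recorded, a simple tabulation of the other ear would let a reader judge that.
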